6.2 GENERAL

This section provides a general overview of the methods. If any of the items require a unique approach that differs from the general overview, then it will be noted in the appropriate section.

All continuous variables will be summarized using the following descriptive statistics: n (non-missing sample size), mean, standard deviation, median, maximum, and minimum. The frequency and percentages (based on the non-missing sample size) of observed levels will be reported for all categorical measures.

All summary tables will be structured with a column for each treatment arm and will be annotated with the total population size relevant to that table/treatment, including any missing observations.

Analyses will follow the principle of intention-to-treat (i.e., based on randomized population).

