6.5.1 Primary Efficacy Endpoint

The primary efficacy objective is to evaluate the clinical effect of prophylactic emicizumab compared with no prophylaxis on the number of bleeds over time. The definition of a bleed is described in Section 4.5.8. The primary endpoint is based on treated bleeds.

The primary efficacy analysis will be conducted after all randomized patients (and a minimum of 40 patients previously treated with prophylactic FVIII) have completed

24 weeks in the study or the last randomized patient yet to complete 24 weeks in the study discontinues study participation, whichever occurs first, and using an intent-to-treat principle. The comparison of the number of bleeds over time between the randomized treatment arms will be performed using an NB regression model, which accounts for different follow-up times, with the patient's number of bleeds as a function of randomization and the time that each patient stays in the study included as an offset in the model. The model also includes the number of bleeds (< 9 or ≥ 9) in the last 24 weeks prior to study entry as a stratification factor in the randomization. This analytic model estimates the rate ratio, λ_t/λ_c , which quantifies the risk of bleeding associated with prophylactic emicizumab (λ_t) in comparison to no prophylaxis (λ_c). Statistical significance is controlled at the 2-sided, 0.05 alpha (α) level. Of note, hierarchical testing is used to account for multiple testing and the first test to be included in the hierarchy is the emicizumab 1.5 mg/kg/wk maintenance dose versus control. The second test will be 3 mg/kg/2wks maintenance dose versus control. The description below covers both hypotheses to be tested:

H_0 (null hypothesis): Rate Ratio = 1 versus H_1 (alternative hypothesis): Rate Ratio $\neq 1$.

The treatment effect therein is based on a contrast statement in the model with use of the SAS GENMOD procedure. Statistical significance at the prespecified alpha level will be based on a Wald testing procedure. Bleed rates for prophylactic emicizumab and no prophylaxis and the rate ratio will be presented and include 95% confidence intervals.

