## **2.2            COLLECTION OF PATIENT-REPORTED DATA**

### **2.2.1            Collection of Bleed and Medication Data**

Bleed and medication data are collected through an electronic bleed and medication questionnaire (BMQ), which was developed by the Sponsor given that no standard questionnaire for collection of these data exists.

The BMQ was developed as a patient-reported measure of bleeding episodes (including cause, type, location, and symptoms of bleeds) and hemophilia-related medication use. The draft questions were developed following review of the hemophilia A literature and discussions with medical professionals regarding what information on related bleeds was most important to capture. Prior to use in this study, qualitative interviews with patients with hemophilia A were conducted in order to evaluate the measure's content validity and to test the understanding and usability of the BMQ on an electronic, handheld device. Cognitive interviews were conducted in person with a total of 20 patients aged 12 years and older with hemophilia A; the results demonstrated that the BMQ was comprehensive and relevant to patients' experiences with bleeds and treatments.

To capture bleed data, emicizumab use, and other hemophilia medication use during study treatment, patients will complete the BMQ on a handheld device that will be provided to them during the Week 1 visit at the study site. This device will remain with the patient for the duration of the study to enter bleed and medication data weekly at a minimum. In case a patient did not experience any bleeds or administer any treatments for a week, the patient is asked to log into the device and fill in the questionnaire to confirm this. These weekly entries, in addition to the bleeds and medication entries, can also be used to assess compliance. Of note, the patient is able to enter bleeds and medications for the past 8 days, including the day the entries are made. This retrospective data entry window was considered acceptable in terms of recall bias and was added in order to optimize the completeness of data collection.

Patients who withdraw from emicizumab treatment will continue to record bleeds and hemophilia medication administration until they complete the safety follow-up visit.

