#### **2.3.1.1 Efficacy Period**

The start of the efficacy period for each individual patient is defined as the first day when there is data in the BMQ. For patients starting the study on emicizumab (Arms A, B, and D) this is expected to coincide with the Week 1 visit, and the day of their first emicizumab dose. For patients who do not start the study on emicizumab (Arm C), the start of the efficacy period should coincide with the Week 1 visit.

Of note, the first day when there is data in the BMQ, includes the first day for which data is reported via the handheld device, a DCR, or the day of device activation.

A second efficacy period is defined for patients in Arm C who switch to emicizumab starting on the day of their first emicizumab dose.

For patients randomized or enrolled on emicizumab, the end of the efficacy period is defined as the date of the clinical cutoff or the date of withdrawal from the initial study period (i.e., treatment phase according to eCRF), whichever is earlier. For patients randomized to no prophylaxis (Arm C), the end of the first efficacy period is defined as the day before the first emicizumab dose or the date of withdrawal from the initial study period (i.e., treatment phase according to eCRF) or the date of the clinical cutoff if

neither of the aforementioned events has taken place. For patients whose dose is up-titrated, the efficacy period on the initial dose (the initial period for patients randomized/enrolled to Arms A, B, and D; the second efficacy period, starting at first emicizumab dose for patients randomized to Arm C) ends 1 day prior to the first day on the up-titrated dose.

For patients who withdraw from the study before reaching the Week 1 visit, the duration of the efficacy period is set to 1 day, and it starts and ends on the day of randomization/enrollment.

For patients whose dose is up-titrated, the bleeds on the up-titrated dose are analyzed separately. The efficacy period on a given up-titrated dose (second efficacy period for patients randomized/enrolled to Arms A, B, and D; third efficacy period for patient randomized to Arm C) starts with the first day on this dose and ends on the day of the clinical cutoff or the date of withdrawal.

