## **2.4 DETERMINATION OF SAMPLE SIZE**

The sample size for this study is based on clinical rather than statistical considerations, taking into account the limited number of patients with hemophilia A without inhibitors available for participation in clinical studies and in an effort to collect sufficient data to assess the safety and efficacy of emicizumab.

The sample size calculation is based on the evaluation of the primary efficacy endpoint, defined as the number of bleeds over time (i.e., bleed rate) with emicizumab (treatment group,  $\lambda_t$ ) versus no prophylaxis (control group,  $\lambda_c$ ), which are said to follow a negative binomial (NB) distribution. With consideration of enrollment feasibility, a sample size of 75 patients, assuming an allocation ratio of 2:2:1 (30 patients in each randomized treatment group and 15 patients in control group), will achieve a power of more than 90% assuming a mean ABR of 4 and 14 bleeds (with variances = mean  $\times$  10) for the emicizumab treatment and control arms respectively, representing an expected 71% reduction in the ABR compared to the control arm. Initial sample size calculations were performed with East®, Version 6 (Cytel, Cambridge, MA), assuming the patients from each treatment group are followed up to 0.5 units of time (i.e., 24 weeks).

However, the above approach to sample size calculation assumes similar follow-up for each patient. Because this is unlikely to be seen in the study, power was also estimated by simulation to account for different follow-up times among patients. Conducting simulations on the basis of an NB regression model including an offset variable to account for variable follow-up times, with all other assumptions remaining the same as previously described, the sample size is projected to have greater than 90% power at the 2-sided 0.05 level of significance.

The analysis will include all enrolled patients regardless of their length of follow-up. Therefore, to ensure the analysis is based on sufficient follow-up data and with 2:2:1 treatment to control randomization, approximately 34 patients in each randomized

[figure not shown]

emicizumab treatment arm (68 in total) and 17 patients in the control arm (approximately 85 patients in total) will be enrolled.

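### Primary follow-up in Arms A and B appears to end at treatment-phase withdrawal, and no planned randomized comparison uses the bleeds recorded after that

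*SAP*

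**What the plan says.** **Principle.** Protocol 6.2 states: "Analyses will follow the principle of intention-to-treat (i.e., based on randomized population"). SAP 4.2.1 likewise defines its ITT population as everyone randomized, analysed by assigned arm, and makes it primary for efficacy.

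**Offset.** Protocol 6.5.1 has "the time that each patient stays in the study included as an offset in the model". SAP 4.5.1 keeps that phrase but equates it with the length of the efficacy period.

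**End of the efficacy period.** For emicizumab patients, SAP 2.3.1.1 takes the earlier of the clinical cutoff and "the date of withdrawal from the initial study period (i.e., treatment phase according to eCRF"). For Arm C the first period ends the day before the first emicizumab dose, at the same kind of withdrawal, or at the cutoff.

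**Data collection.** SAP 2.2.1 says: "Patients who withdraw from emicizumab treatment will continue to record bleeds and hemophilia medication administration until they complete the safety follow-up visit". Protocol 4.5.7, 4.6.2 and Appendix 1 (footnote m) agree, and 4.6.2 places that visit 24 weeks after the last dose.

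**Visit structure.** The notes to the schedule of assessments (Protocol Appendix 1, SAP Appendix 2) tie the study completion evaluation to stopping emicizumab or moving to another study.

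**Sensitivity analyses.** One item in SAP 4.5.4 limits the analysis to the first 24 weeks. It counts patients who withdraw from study treatment only until that withdrawal.

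**The concern.** The trial asks patients who stop emicizumab to go on recording bleeds for about half a year, but the analysis of the primary endpoint appears to use none of those records. If a patient stops because of bleeding or intolerance, both bleeds and time leave the model just when the bleed rate may rise.

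The cut is also uneven. Before its switch Arm C has no study drug to stop, so truncation at drug discontinuation falls mainly on Arms A and B. The trial is open-label, so the decision to stop may depend on perceived response. At stake are the size of the reported rate ratio and how it is read: a reader who sees ITT will probably assume that follow-up continued after treatment stopped.

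**Working it through.** **1. Does stopping emicizumab end the efficacy period?** SAP 2.3.1.1 points to the treatment phase recorded on the eCRF. The schedule notes place the completion evaluation at emicizumab discontinuation, with the safety visit 24 weeks later. Together these indicate that the treatment phase ends when the drug is stopped. This is a strong inference, because the eCRF is not among the documents.

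**2. Does any listed analysis restore the later bleeds?** The SAP 4.5.4 item on all bleeds recorded in the device is explained there as dropping the 72-hour rule; it does not change the efficacy period. The 24-week item stops at treatment withdrawal. The remaining items change the bleed definition, the patients included or the model. None adds later bleeds to A versus C or B versus C.

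**3. The plan's own figure.** SAP 2.4 claims power of more than 90%, "assuming a mean ABR of 4 and 14 bleeds", with variance 10 times the mean, 30 versus 15 patients and 0.5 year.
- Negative binomial dispersion k = 9/mean: 9/4 = 2.25 and 9/14 = 0.643.
- SE² = (1/(0.5×4) + 2.25)/30 + (1/(0.5×14) + 0.643)/15 = 0.0917 + 0.0524 = 0.1441, so SE = 0.380.
- Power = Φ(ln(14/4)/0.380 − 1.96) = Φ(1.34) = 0.91. With 34 versus 17 it is 0.94.
- Rate ratio 4/14 = 0.286, which matches "representing an expected 71% reduction in the ABR compared to the control arm".

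The figure reproduces with arm-specific dispersion on the annual scale. Some other readings of the variance rule give less, which is a separate matter and does not affect the ratios below. The calculation applies one emicizumab rate throughout, so it cannot distinguish the two ways of counting follow-up.

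**4. Illustration over 24 weeks.** Let a fraction p of an emicizumab arm stop at Week w, with mean rate m from then to Week 24. Counting everything recorded,

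rate = 4 + p × (24 − w)/24 × (m − 4), and ratio = rate/14.

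- Immediate return: m = 14.
- Gradual washout: the rate u weeks after stopping is 14 − 10 × 2^(−u/h). With L = 24 − w, m = 14 − 10 × [h/(L ln 2)] × (1 − 2^(−L/h)). Protocol 1.2.2 gives a half-life h of 4 to 5 weeks; that the bleed rate follows it is an assumption.

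For w = 8 (L = 16), m = 10.62 at h = 4 and 9.98 at h = 5. With p = 0.10:
- gradual, h = 4: 4 + 0.1 × (16/24) × 6.62 = 4.44, ratio 0.317;
- gradual, h = 5: 4 + 0.1 × (16/24) × 5.98 = 4.40, ratio 0.314;
- immediate: 4 + 0.1 × (16/24) × 10 = 4.67, ratio 0.333.

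For w = 12 (L = 12), m = 9.79 at h = 4 and 9.13 at h = 5.

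| Assumed stopping | Truncated ratio | Gradual washout | Immediate return |
|---|---|---|---|
| 1 of 34 at Week 12 | 0.286 | 0.291–0.292 | 0.296 |
| 3 of 34 at Week 8 | 0.286 | 0.311–0.314 | 0.328 |
| 10% at Week 8 | 0.286 | 0.314–0.317 | 0.333 |
| 20% at Week 12 | 0.286 | 0.322–0.327 | 0.357 |

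For 10% at Week 8 the ratio rises by 10–11% (gradual) to 17% (immediate). Putting 4.40–4.44 or 4.67 into the step 3 formula with 34 versus 17 and unchanged dispersion gives power of about 0.90 or 0.87.

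**5. Are the data there?** Someone who stops at Week w is due to record to Week w + 24, which is beyond Week 24. Consent withdrawal is the exception: Protocol 4.6.1 ends follow-up then.

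**The case against.** **The label is used as defined.** Protocol 6.2 explains intention-to-treat as based on the randomized population, and the SAP meets that. It also states its offset and its efficacy period openly. This stands. A reader might infer that the primary analysis is not ITT, but the documents do not support that; only the follow-up is in question.

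**The treatment phase may mean a study period rather than drug exposure.** The same wording is applied to Arm C while it has no study drug. The explicit stop in the 24-week sensitivity item would also be redundant if the primary analysis already stopped there. This is a fair reason to ask for clarification, but the schedule notes point the other way. Calling the analysis strictly on-treatment would still go too far, since nothing in SAP 2.3.1.1 removes missed doses or temporary interruptions.

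**Immediate return to 14 per year is a worst case.** This stands, given the half-life. Even the washout figures may be high. Protocol Table 1 shows a mean reduction of 74.5% at 0.3 mg/kg/week, one-fifth of the weekly maintenance dose, and falling to one-fifth takes about 9 to 12 weeks (log2 5 = 2.32 half-lives). That group had only six patients, two of whom later escalated.

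**The stopping rates have no source, and the window differs.** Both are true. Primary follow-up runs to the clinical cutoff, 6 to 12 months or longer on emicizumab (Protocol 3.3.4), so a 24-week illustration does not measure the bias in the primary estimate. The direction is not certain either: a patient who stops may move to other prophylaxis.

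**Conclusion.** The gap is real but limited. The population is ITT, follow-up for Arms A and B appears to end at treatment-phase withdrawal, and bleeds that the trial goes on collecting enter no planned randomized comparison. This could favour emicizumab.

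The size depends on a discontinuation rate that the documents do not give. Under the planning rates over 24 weeks, one patient of 34 stopping moves the ratio by 0.005 to 0.010, and 10% stopping at Week 8 moves it by about 0.03 to 0.05. A reader might conclude that the primary result is in doubt. The figures do not support that: every ratio in the table stays far below 1, and at low stopping rates the conclusion is unlikely to change. What is affected is the effect estimate and what it describes.

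The conclusion rests on reading treatment-phase withdrawal as stopping emicizumab. If the sponsor means withdrawal from the study, saying so would remove most of the concern.

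**What to change.** 1. Add to SAP 4.5.4 a supplementary treatment-policy analysis for A versus C and B versus C. Count all recorded treated bleeds and all time to Week 24 regardless of treatment discontinuation. Follow Arm C until its switch, and count patients who withdraw consent to their last recorded data. Report it next to the primary result.
2. State in SAP 2.3.1.1 what treatment-phase withdrawal means, and that primary follow-up ends there, so that ITT describes the population and not the follow-up.

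The cost is one more run of the primary model on data already being collected, and a few lines of SAP text. The primary test, the testing hierarchy and the sample size do not change.

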The primary efficacy analysis to assess the effect of emicizumab on bleed rate reduction will be performed at the earliest timepoint when all randomized patients (Arms A, B, and C) and a minimum of 40 patients from Arm D have either completed 24 weeks of study treatment or discontinued from the study. Indeed, a similar follow up period was utilized in recent studies that investigated the safety and efficacy of novel FVIII formulations (Mahlangu et al. 2014; Kavakli et al. 2015; Konkle et al. 2015). Further, patients who experience frequent bleeds may not find it acceptable to be randomized to their usual episodic FVIII therapy for longer than 24 weeks prior to receive emicizumab. For this reason, individual patients in the control arm will be offered the opportunity to switch to emicizumab after 24 weeks in the study.

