The patient is able to edit and delete bleeds and medications for 24 hours after they are entered. Furthermore, the investigator and patient are instructed to review the data together at every clinic visit. If the patient has been unable to enter data for any reason, the investigator is able to do so using a data clarification request (DCR; not subject to the previous 8-day data entry window). Note, the symptoms of joint and muscle bleeds are not collected in this case because the patient may not be able to reliably remember them. In addition, the investigator is able to request a change be made to the vendor's database by submitting a DCR.

Furthermore, the Sponsor's data manager and Medical Monitor review the patient entered data for clear inconsistencies against data collected on the electronic Case Report Form (eCRF) or to identify obvious data points to be clarified (e.g., missing entry of the weekly emicizumab injection). These requests are sent to the investigator, who reviews them with the patient and may enter the data via the site data entry system or request a change to be made in the vendor's database via a DCR, if necessary.

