#### **4.5.1 Primary Efficacy Endpoint**

The primary efficacy objective is to evaluate the clinical effect of prophylactic emicizumab compared with no prophylaxis on the number of bleeds over time. The definition of a bleed is described in Section [2.3.1](#). The primary endpoint is based on treated bleeds.

The comparison of the number of bleeds over time between the randomized treatment arms will be performed using an NB regression model, which accounts for different follow-up times, with the patient’s number of bleeds as a function of randomization and the time that each patient stays in the study (the length of the efficacy period) included as an offset in the model. The model also includes the number of bleeds ( $<9$  or  $\geq 9$  according to the eCRF data) in the last 24 weeks prior to study entry as a stratification factor. This analytic model estimates the rate ratio,  $\lambda_t/\lambda_c$ , which quantifies the risk of bleeding associated with prophylactic emicizumab ( $\lambda_t$ ) in comparison to no prophylaxis ( $\lambda_c$ ). Statistical significance is controlled at the 2-sided, 0.05 alpha ( $\alpha$ ) level.

Of note, hierarchical testing is used to account for multiple testing and the first test to be included in the hierarchy is the emicizumab 1.5 mg/kg/wk maintenance dose versus

control. The second test will be 3 mg/kg/2wks maintenance dose versus control. A global approach using a model statement (within GENMOD) with a 3-level categorical effect for treatment (“1.5 mg/kg/wk,” “3 mg/kg/2wks,” or “no prophylaxis”) and an appropriate contrast statement will allow both tests to be performed via the following hypothesis

$H_0$  (null hypothesis): Rate Ratio = 1 versus  $H_1$  (alternative hypothesis): Rate Ratio  $\neq$  1.

Statistical significance at the prespecified  $\alpha$  level will be based on a Wald testing procedure. Bleed rates for prophylactic emicizumab and no prophylaxis and the rate ratio will be presented and include 95% CIs.

The number of bleeds can also be annualized for each patient using the following formula:

$$ABR = (\text{Number of bleeds} / \text{Total number of days during the efficacy period}) \times 365.25.$$

Both the model-based method (estimated ABR from the NB model) and the method using the above formula (calculated ABR) will be used to describe the study results.

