If the NB model converges, the Van Elteren test to compare the mean ABR between the randomized arms will be provided as a sensitivity analysis. However, if the convergence of the NB model is not achieved or is questionable or no bleeds at all were observed in one of the treatment arms, the primary efficacy analysis will be based on the Van Elteren test of ABR, according to the above formula.

Of note, the Van Elteren test will be applied separately for the Arm A versus Arm  $C_{\text{control}}$  (using only patients randomized to Arms A and  $C_{\text{control}}$ ) and for the Arm B versus Arm  $C_{\text{control}}$  comparisons.

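### The 1-day efficacy period for patients withdrawn before Week 1 almost always scores them as ABR 0, at full weight, in the Van Elteren test and the calculated ABRs

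*SAP*

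**What the plan says.** SAP 2.3.1.1 (Efficacy Period) states: "For patients who withdraw from the study before reaching the Week 1 visit, the duration of the efficacy period is set to 1 day". That day is the day of randomisation or enrolment. SAP 2.2.1 explains how bleeds are captured: "patients will complete the BMQ on a handheld device that will be provided to them during the Week 1 visit at the study site". Investigators can also enter data through a data clarification request (DCR). For the start of the efficacy period, the first day with diary data "includes the first day for which data is reported via the handheld device, a DCR, or the day of device activation".

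SAP 4.5.1 gives the primary analysis as NB regression with the length of the efficacy period as offset. It adds: "The number of bleeds can also be annualized for each patient using the following formula", namely bleeds divided by days in the period, times 365.25, with no minimum follow-up. Both the model-based and the calculated ABR are used to describe results. If the NB model converges, the Van Elteren test of ABR is a sensitivity analysis. If convergence fails or is questionable, or an arm has no bleeds, "the primary efficacy analysis will be based on the Van Elteren test of ABR".

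Nothing elsewhere removes or imputes these patients. SAP 4.2.1 and 4.2.2 keep everyone randomised or assigned, and SAP 4.9 treats the bleed data as complete. SAP 2.3.2 and 4.5.2 carry the same efficacy period and the same Van Elteren fallback to all bleeds and to treated spontaneous, joint and target joint bleeds. SAP 4.2.5, in contrast, leaves these patients out of the safety population, which needs a dose in Arms A, B and D or a Week 1 visit in Arm C.

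**The concern.** A patient who was never followed enters the rank test as if followed without a bleed. Randomised patients must have had at least 5 bleeds in the previous 24 weeks (Protocol 4.1.1), which is an ABR of at least 5 / 168 x 365.25 = 10.9. Withdrawal before Week 1 turns that into 0.

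The NB offset discounts a short period. A rank test on individual ABRs does not, and neither does a mean of individual ABRs. The direction depends on the arm: a zero in Arm C works against emicizumab, and a zero in Arm A or B works for it. At stake are the sensitivity analysis, the descriptive ABRs and, if the fallback is triggered, the primary or a secondary test. A backup analysis should not be more fragile than the model it backs up.

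**Working it through.** **Inputs.** SAP 2.4: ABR 4 (emicizumab) and 14 (control), variance 10 x mean, two-sided 0.05, 24 weeks taken as 0.5 year, 30 vs 15 patients per comparison for power, 34 vs 17 planned. The number of withdrawals before Week 1 is not in the documents, so 0 to 3 per arm is an assumption.

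**The plan's own figure.** Reading the variance as annual and arm-specific, the dispersions are (40 - 4)/4² = 2.25 and (140 - 14)/14² = 0.643. The variance of the log rate ratio is (1/(4 x 0.5) + 2.25)/30 + (1/(14 x 0.5) + 0.643)/15 = 0.0917 + 0.0524 = 0.1441, so SE = 0.380. Then ln(14/4)/SE = 1.253/0.380 = 3.30, and power = Φ(3.30 - 1.96) = 0.91. This reproduces the stated figure of more than 90% (0.94 at 34 vs 17). Other readings of the variance give 0.69 to 0.99, so this reading is used below.

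**Score of a 1-day patient.** No bleed gives 0/1 x 365.25 = 0; one bleed gives 365.25. With mean m and dispersion k, the chance of any bleed in one day is 1 - (1 + k·m/365.25)^(-1/k): 1.1% at ABR 4 and 3.7% at ABR 14. So 96-99% score 0 even if every bleed is recorded. Over a real 168 days, the expected share with no bleed is 48% on emicizumab and 8% on control, so a false zero is more out of place in Arm C.

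**NB model.** Each patient's information is μ/(1 + k·μ), with μ the expected count. One day against 168 days: 0.0107/0.358 on emicizumab and 0.0374/1.253 on control, both 3.0%.

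**Mean calculated ABR.** Arm C with 1, 2 or 3 zeros among 17: 14 x 16/17 = 13.2, 14 x 15/17 = 12.4, 14 x 14/17 = 11.5. Arm A with 1, 2 or 3 among 34: 3.88, 3.76, 3.65.

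**Rank-test power, 34 vs 17.** The stratified runs are Van Elteren tests with two equal, non-prognostic strata, emicizumab follow-up uniform over 168-365 days, control follow-up 168 days, and 4,000 runs. The unstratified runs are rank-sum tests with 24 weeks in both arms and 6,000-8,000 runs.

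| Control zeros | Stratified, scored 0 | Unstratified, scored 0 | Left out (stratified / unstratified) |
|---|---|---|---|
| 0 | 97.4% | 98.1% | - |
| 1 | 94.0% | 95.1% | 97.3% / not run |
| 2 | 87.2% | 89.3% | 96.5% / 96.9% |
| 3 | 73.5% | 78.6% | 96.0% / 96.6% |

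One to three zeros in Arm A instead push stratified power up slightly, to 98.4-98.9%.

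**No treatment effect.** With ABR 14 in both arms, 168 days and 8,000 stratified runs, the rejection rate in favour of emicizumab (nominal 2.5%) is 2.1% with no zeros and 3.3%, 4.2% and 5.9% with 1, 2 and 3 emicizumab zeros. With 1 or 2 control zeros it is 0.7% or 0.2%. Leaving the patients out gives 2.3-2.6%.

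**The case against.** The strongest reply is that the affected group should be nearly empty. Protocol 3.1 puts enrolment and arm assignment at the Week 1 visit, on the day the first dose is due. Three of 17 controls would be 18% of the arm, and no document supports a count that high. This stands, and it limits the size of the point. It does not make the rule right for the patients it was written to cover.

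The primary NB analysis is also practically immune. For treated bleeds, the no-bleeds trigger is remote: with 48% bleed-free patients, the chance that all 34 in an arm are bleed-free is about 0.48^34, or roughly 10^-11. This stands too. The trigger is less remote for the joint and spontaneous subsets, and the sensitivity analysis and calculated ABRs are reported in any case.

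SAP 4.5.4 lists a sensitivity analysis restricted to patients with at least 12 weeks of emicizumab. It would drop emicizumab non-starters, but it is run only if needed and does not address controls.

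A reader might go further in three ways that the documents do not support:

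- **That such a patient has no means of recording a bleed.** The DCR route exists and counts as diary data. The zero comes from the 1-day window itself.
- **That the protocol expects early refusal of the control arm.** Protocol 3.3 says "patients who experience frequent bleeds may not find it acceptable to be randomized to their usual episodic FVIII therapy", but the sentence goes on to limit this to periods beyond 24 weeks. It explains the offer to switch and is no evidence that non-starters cluster in Arm C.
- **That the trial's type I error is inflated.** The 5.9% belongs to a test that decides nothing unless the fallback is triggered.

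**Conclusion.** The point holds for the Van Elteren test and the calculated ABRs of the bleed endpoints; it does not hold for the NB primary analysis. The written rule scores a patient with no real follow-up as ABR 0 in 96-99% of cases and gives that score full weight.

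Per patient, the effect is largest in the control arm. Van Elteren power goes from 97-98% with none to 94-95% with one and 87-89% with two, against about 97% if the two are left out. Mean calculated control ABR falls from 14.0 to 12.4 with two. In the other direction, three emicizumab zeros under no effect raise rejection favouring emicizumab to about 6%.

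These figures rest on the plan's rates and variance, 34 vs 17 patients, non-prognostic strata and assumed counts of withdrawals. The likely count is zero or close to it, so this is a gap to close before the analysis and no threat to the main conclusion.

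**What to change.** Keep these patients in the NB model as planned. In SAP 4.5.1, with a reference from the bleed-related secondary endpoints, add that patients with no observed efficacy period beyond the assigned 1 day are left out of the Van Elteren test and of the calculated-ABR summaries, that their number is reported by arm, and that the all-randomised version is shown alongside.

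Imputing the pre-study ABR from the 24-week count is a less sound alternative. SAP 2.3.2.5 limits historical comparison to patients from the non-interventional study, because only there are bleeds recorded in enough detail. Protocol 3.3 calls routine bleed recording incomplete. A total count also gives no value for joint or spontaneous bleeds.

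The change takes a few sentences and no new data. Its cost is that these analyses omit a few randomised patients, who stay in the NB analysis. If the fallback makes Van Elteren primary, the omission departs from full intention-to-treat, which is why the all-randomised result should stand next to it.
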